13.6 Analysis of Covariates

Descriptive statistics will be performed for baseline covariate data, including summary statistics (e.g., mean, median, standard deviation, quartiles, range) to identify extreme outliers. We will examine if covariates are balanced between study groups.

13.7 Exploratory Analysis

In exploratory subgroup analyses, we will apply the GEE models for the primary analysis given above to study the intervention effect on each of the primary outcomes among participants who developed (versus those who did not develop) recurrence over the course of the study. The GEE models will also be applied to additional exploratory subgroup analyses to assess the intervention effects on the primary outcomes by chemotherapy maintenance group (if the sample size is sufficient).

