The biobehavioral mechanisms through which physical activity may decrease mortality in cancer survivors are unknown. We will investigate the potential role of exercise in reversing biologically harmful effects of psychological distress. Psychological distress is common in ovarian cancer survivors (2-5), and chronic stress/distress may promote cancer growth through prolonged activation of the Hypothalamic Pituitary Adrenal axis and of the sympathetic nervous system, resulting in excess secretion of cortisol and norepinephrine, respectively (22-24). This in turn alters expression of cytokines such as interleukin-6 (IL-6) and vascular endothelial growth factor (VEGF), which are involved in angiogenesis and tumor invasion (25-27). Cortisol also has direct effects on tumor growth (28, 29). Psychological distress, depression, and poor social support are associated with elevated serum IL-6, VEGF, evening salivary cortisol, and elevated tumor norepinephrine levels in ovarian cancer survivors (30-34). Elevated IL-6, VEGF, and salivary evening cortisol all predict worse survival in ovarian cancer patients (N=90 to 314) (35-38). Increased *ADRB2* gene expression is also associated with decreased ovarian cancer survival (39), and non-selective beta-blocker use is associated with improved survival (40, 41). Studies using animal models of breast and prostate cancer suggest that exercise may decrease tumor growth (42-44), modulate expression of prometastatic genes with a shift towards reduced metastasis (45), and decrease IL-6 and VEGF (42, 44, 45). Limited clinical studies also suggest exercise decreases VEGF, IL-6, and improves diurnal cortisol in cancer survivors (46-48). Combined exercise and diet interventions in persons without cancer have also been shown to decrease serum IL-6 (49-51). Exercise decreases serum norepinephrine in women with fibromyalgia (52).

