The data from this R21 project will justify a larger randomized controlled trial of a moderate exercise intervention in OC survivors that will be powered to detect a difference in progression-free survival and further elucidate biobehavioral pathways through which physical activity may affect cancer prognosis and survival. This study would significantly differ from the NCTN/NCORP randomized controlled trial that is testing diet, weight maintenance, and low-level physical activity on quality of life and progression-free survival (53). As some randomized controlled trials have suggested that moderate activity is more important than low-level activity (8), our study provides additional value. The majority of individuals with ovarian cancer experience poor quality of life (4) and ultimately die of their disease despite conventional therapy. Determining if exercise can improve quality of life and survival would have a significant impact on people with ovarian cancer.

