3.3 Study Design

Individuals with stage II-IV ovarian cancer (N=98) who have completed primary treatment within one to six months and are in clinical remission will be randomized in a 1:1 ratio to a 24-week home-based exercise program or wait-list control. The exercise prescription will consist of 150 minutes of moderate aerobic exercise (the equivalent of brisk walking or higher intensity) per week, with weekly telephone-based support by an exercise physiologist. The control group will perform their usual activities and will be offered the exercise intervention after 24 weeks. Baseline and 24-week assessments will include validated questionnaires assessing distress and health-related quality of life, serum levels of IL-6 and VEGF, salivary cortisol levels measured at bedtime for three consecutive days, and 24-hour urinary norepinephrine levels. Participants will also complete questionnaires at 12 weeks to provide additional longitudinal data. Adherence to the intervention will be assessed by daily activity logs, actigraphs, and completion of weekly telephone calls.

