9.0 SUBJECT DISCONTINUATION FROM STUDY

Subjects may be removed from this study at any time at their discretion. Subjects may also be removed from this protocol if they develop any untoward side effects from the study intervention.

Cancer recurrence does not mandate study discontinuation. If a subject develops cancer recurrence, they may still continue on the study if they are willing and able. Exercise is safe for individuals with cancer who are undergoing active treatments including chemotherapy. The exercise physiologist may alter their exercise prescription as needed based on the individual's functional ability and medical condition. If a participant desires to discontinue the study, she may discontinue the study at any time. If an individual desires to stop exercising but is willing to complete study assessments, she will complete originally planned study assessments (including clinic visit) at the originally specified time points.

An explanation for discontinuing the study is recorded for each subject discontinuing the study on the appropriate CRF/eCRF. Treatment in this study must be discontinued for any of the following reasons:

- if the PI decides to stop the study;
- at Investigator's discretion;
- at the subject's request;
- Grade 4 or life-threatening toxicity (See Section 11, Adverse Events) attributable to study intervention

Target enrollment is 98 participants, accounting for up to 20% drop-out. Power calculations are based on 78 participants. Additional subjects may be enrolled in the study to replace individuals who have dropped out in order to achieve the goal of 78 participants completing the study.

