13.4 Randomization

After baseline assessments are complete, participants will be randomized with equal probability to the exercise intervention (N=49) or wait-list control (N=49). Randomization will be blocked on stage (stages II-IIIA vs. IIIB-IV) and body mass index (<30 kg/m² vs. \geq 30 kg/m²) and will use permuted blocks with random size.

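### The planned recurrence subgroup in Section 13.7 conditions on an event after randomisation, so its within-group estimates should be reported as descriptive and not as intervention effects

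*Combined protocol and SAP*

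**What the plan says.** Section 13.7 (Exploratory Analysis) states: "we will apply the GEE models for the primary analysis given above to study the intervention effect on each of the primary outcomes", and defines the subgroups as those "among participants who developed (versus those who did not develop) recurrence over the course of the study". By Section 13.2, the quantity estimated is β₁, the difference between arms in mean change from baseline to 24 weeks. With seven primary outcomes and two groups, that makes 14 such estimates.

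Four other places bear on the point.

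- Section 3.3 describes the population as those "who have completed primary treatment within one to six months and are in clinical remission will be randomized in a 1:1 ratio". Nobody has recurrent disease at baseline.
- Section 13.4: "Randomization will be blocked on stage (stages II-IIIA vs. IIIB-IV) and body mass index". Recurrence is not a randomisation factor and, as a later event, could not be one.
- Section 9.0: "Cancer recurrence does not mandate study discontinuation". Participants who recur may stay on study, so some outcome data will exist in that group.
- Section 2.1 hopes for a later, larger trial that "will be powered to detect a difference in progression-free survival". It also says: "Elevated IL-6, VEGF, and salivary evening cortisol all predict worse survival in ovarian cancer patients". All three markers are primary outcomes here.

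Section 13.7 calls the analysis exploratory. I found no caveat about subgroups formed after randomisation, no causal method such as principal stratification, and no interaction test.

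**The concern.** Randomisation makes the arms comparable as randomised. It does not make exercise recurrers comparable with control recurrers, or the two sets of non-recurrers comparable with each other.

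Suppose exercise prevented some recurrences. Those who still recurred on exercise would then tend to have worse underlying disease than control recurrers. The exercise non-recurrers would include people who would have recurred without exercise, so they too would be a less healthy group than control non-recurrers. If underlying disease also affects the outcome, a difference between arms appears in both groups even when exercise does nothing to that outcome.

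Detection that differs by arm can act in the same way. During the 24 weeks, the weekly calls go only to the exercise arm (Section 7.2, Appendix C). I found no schedule for ascertaining recurrence, and Section 15.3 names only a baseline medical-record review form.

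What is at stake is interpretation: a reader could take a within-group β₁ as evidence that exercise does, or does not, help after recurrence.

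**Working it through.** **1. The plan's own figure.** Inputs from Section 13.3, Table 1: SD 9.2 for the SF-36 physical component score (PCS), 39 per arm, ρ = 0.5, power 80%, α = 0.05/7 = 0.00714. Tests are two-sided (Section 13.2).

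Detectable difference = (z for α + z for power) × SD × √(2(1−ρ)) × √(2/n)
= (2.690 + 0.842) × 9.2 × 1 × √(2/39) = 7.36.

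Table 1 prints 7.36. At ρ = 0.65 and 0.8 the formula gives 6.16 and 4.65, also as printed. In SD units the first figure is 7.36/9.2 = 0.80.

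**2. Size of the bias.** The documents give neither a recurrence rate nor a 24-week effect of exercise on recurrence, so everything in this step is assumed. The simulation used 2,000,000 people per scenario and no exercise effect on PCS change for anyone. A latent disease factor was correlated 0.3 or 0.5 with PCS change and acted on recurrence with a log-odds slope of 1 or 2. Control recurrence was 15%, 30% or 50%. Exercise multiplied the odds of recurrence by the ratio shown. The entries are spurious differences in PCS points, exercise minus control, as ranges over the scenarios.

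| Odds ratio | Recurrers | Non-recurrers |
|---|---|---|
| 1.0 | −0.03 to +0.05 | −0.05 to +0.03 |
| 0.7 | −0.13 to −0.38 | −0.09 to −0.29 |
| 0.5 | −0.21 to −0.64 | −0.15 to −0.58 |
| 0.3 | −0.31 to −1.11 | −0.23 to −0.93 |

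The comparison of all randomised participants stayed within 0.04 of zero in every scenario. At odds ratio 1.0 the values are simulation noise. For ratios of 0.7 to 0.3 the bias runs from 0.09/9.2 = 0.01 SD to 1.11/9.2 = 0.12 SD.

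**3. False positives.** With 39 per arm, 30% control recurrence and the stronger link (correlation 0.5, slope 2), a two-sample t-test on change at nominal 5% rejected as follows in recurrers and non-recurrers: 5.0% and 5.1% at odds ratio 1.0, 5.0% and 5.3% at 0.5, and 5.5% and 6.1% at 0.3. These rates isolate the selection bias. They do not assess how the planned large-sample Z-test behaves in very small groups.

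**4. Sparse data.** Assume 4 to 10 recurrers per arm (8 to 20 of 78, or 10% to 26%). At α = 0.05, in SD units, the detectable difference is (1.960 + 0.842) × √(2(1−ρ)) × √(2/n):

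| ρ | n = 4 per arm | n = 10 per arm |
|---|---|---|
| 0.5 | 1.98 | 1.25 |
| 0.65 | 1.66 | 1.05 |
| 0.8 | 1.25 | 0.79 |

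At the higher recurrence rates of step 2 the group is larger. With 30% in both arms, n = 11.7 per arm and the detectable PCS difference at ρ = 0.5 is 10.7 points at α = 0.05 (13.4 at 0.05/7). With 50%, n = 19.5 and it is 8.25 points at α = 0.05, or 0.90 SD. Section 13.7 attaches a sample-size condition to the maintenance-therapy subgroup but not to the recurrence subgroup.

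**The case against.** The strongest reply is that this hardly matters in practice. The analysis is labelled exploratory, feeds no primary endpoint and triggers no decision, and outcomes in people who relapse are of natural interest. The bias needs an effect on recurrence, or on its detection, within 24 weeks. The sample exercise progression in Section 7.2 reaches its full weekly goal only at week 8. Even the extreme scenario gives 1.1 points against a full-sample detectable difference of 7.36. All of this stands, and it limits the severity.

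A reader might go further and infer that the protocol itself expects exercise to change recurrence in this trial, so that the subgroup estimates must be biased. The documents do not support that. Section 2.1 refers to progression-free survival only as the target of a later trial, and recurrence is not among the objectives in Section 3.1. The nearest figures in Section 2.1 are 26% and 32% lower cancer mortality (the latter not statistically significant), from an observational study of activity measured years before diagnosis. They concern a different endpoint and a different exposure period.

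A reader might also infer a serious risk of false findings from the bias alone. Rejection rates of at most about 6% do not bear that out.

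What the reply does not remove is the logical point. The exploratory label warns about multiplicity and low power. It does not tell a reader that the comparison is no longer a randomised one.

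**Conclusion.** The point holds as a matter of design logic. Section 13.7 treats as an intervention effect a contrast that randomisation does not protect. The estimates in both groups are biased if exercise, or contact that differs by arm, alters the occurrence or detection of recurrence within 24 weeks. They are unbiased in expectation if neither does, and the documents do not settle which.

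Under the assumptions of the working, the bias is small and lack of precision in the recurrence group is at least as large a problem. Both sizes rest on assumed recurrence figures. The primary comparison of all randomised participants is not touched. Severity is low to moderate.

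**What to change.** In Section 13.7, delete the GEE treatment-effect estimates and tests by recurrence status. Instead, report change in each primary outcome by arm and recurrence status as summary statistics only, with a sentence that these groups arise after randomisation and that the figures are descriptive and do not estimate the intervention effect. The sentence is essential, because an unlabelled table would invite the same conditioned comparison. Section 9.0 already allows assessments to continue after recurrence, so data collection does not change.

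If effect modification by prognosis is wanted, add an exploratory model using the existing baseline randomisation factor, stage II-IIIA versus IIIB-IV. In the notation of Section 13.2, with S for stage, add S, S·j, X·S and X·S·j. The coefficient of X·S·j measures how the intervention effect differs by stage.

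The cost is a few lines of SAP text. One exploratory model-based estimate is lost, and the stage analysis answers a related but different question.

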5.0 SUBJECT ELIGIBILITY

5.1 Inclusion Criteria

5.1.1 Histologically or cytologically confirmed stage II-IV primary epithelial ovarian, fallopian tube, or peritoneal cancer. If site of origin cannot be specified, carcinoma of Mullerian origin may be included if most consistent with ovarian/fallopian tube/peritoneal origin rather than uterine origin. The following histologic epithelial cell types are eligible: serous adenocarcinoma, endometrioid adenocarcinoma, mucinous adenocarcinoma, clear cell carcinoma, mixed epithelial carcinoma, transitional cell carcinoma, malignant Brenner's tumor, undifferentiated carcinoma, carcinosarcoma, or adenocarcinoma not otherwise specified. Individuals with neoplasms of low malignant potential (borderline tumors) are not eligible.

5.1.2 Subjects must have no evidence of disease, as defined by their treating oncologist, and with normal CA-125 (≤ 35).

5.1.3 Subjects must have completed primary surgery and adjuvant chemotherapy for treatment of ovarian, fallopian tube, or peritoneal cancer within one to six months of screening. Maintenance therapy will be allowed as long as the participant is in clinical remission— including hormonal agents, anti-angiogenesis agents, PARP inhibitors, and immunotherapy. Prior radiation therapy is allowed, as long as it has been completed within one to six months of screening. Subjects may have received prior therapies (including surgery, chemotherapy, radiation therapy) for other malignancies in the past.

5.1.4 Subjects must be 18 or older.

5.1.5 ECOG status of 0, 1, or 2. See Appendix B.

5.1.6 Pregnancy and the need for contraception:
N/A – participants with ovarian cancer have undergone hysterectomy with removal of ovaries and tubes as part of surgical treatment, and therefore do not have the potential to become pregnant.

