13.2 Primary/Secondary Endpoints/Hypotheses and Analytical Methods

Descriptive statistics will be performed for baseline data, and distributions of outcome measures will be characterized using scatterplots, histograms, and summary statistics (e.g., mean, median, standard deviation, quartiles, range) to identify extreme outliers. Outcome variables will be log-transformed if their distributions are not symmetric. We will also examine if these measurements are balanced between the study intervention groups. The primary assessment of the exercise intervention effects will compare the average change from baseline to 24-week follow-up outcome measures (such as SF-36 physical component score) between the exercise group and the control group. Analyses will be intention-to-treat. The generalized estimating equations (GEE) modification of linear regression will be used in order to model the relationship between the outcome measures and exercise intervention and to account for the correlation within individual data over time. The GEE model will adjust for the measurement time and other potential covariates. Prior to fitting the GEE model, logarithmic transformation will be applied (if appropriate) to the outcome data to achieve approximate normality and variance stabilization. Our statistical inference on each outcome will use the standard large-sample approximation, namely, two-sided Z-test and Z-confidence intervals based on the limiting Gaussian distribution. More specifically, for the primary comparison between exercise group *vs.* control group, let Y_{ij} be the outcome measure (or log-transformed if appropriate) of interest for participant i at time j , where j is 0 for baseline and 1 for 24 week follow-up, X_i be the indicator variable for the intervention status (1=intervention, 0=control) and Z_i represent a vector of other potential adjusting variables (such as age, BMI). The linear model is as follows:

$$E[Y_{ij}] = \alpha_0 + \alpha_1 j + \beta_0 X_i + \beta_1 X_i j + \gamma^T Z_i, \text{Var}[Y_{ij}] = \sigma^2 \text{ and } \text{Cov}[Y_{ij}, Y_{kl}] = \rho \text{ if } i = k \text{ and } j \neq l, \text{ and } 0 \text{ otherwise.}$$

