The parameter β_1 is of our main interest and represents the mean difference in the outcome change from baseline to follow-up between participants in the exercise group and participants in the control group, adjusting for covariates Z such as age and BMI. We will first assess β_1 without any adjustments for Z (unadjusted analysis), and then add Z (adjusted analysis). Under the null hypothesis of no difference between intervention and control on the changes in the outcome measure, β_1 is equal to zero. If the exercise intervention indeed results in a greater reduction/increase in the outcome measure of interest in the exercise group compared with the control group, then β_1 is different from zero. Our statistical inference on β_1 will use the standard large-sample approximation, namely, two-sided Z-test and Z-confidence intervals based on the limiting Gaussian distribution.

Our analysis will be based primarily on intention-to-treat principle, but with minor modifications for practical considerations. The principles of ITT analyses are (i) keep participants in the intervention groups to which they were randomized, regardless of the intervention they actually received; (ii) measure outcome data on all participants; and (iii) include all randomized participants in the analysis (107). However, if data of individuals are lost, or are unavailable for other reasons immediately after randomization, then we will not include these individuals in the analysis (modified intention-to-treat). Under the modified intention-to-treat principle, enrolled participants who were later found to be ineligible will not be included in the primary analysis. To take adherence into account, we will also perform per-protocol analysis which includes only individuals who are considered adherent to the intervention assignment. Per-protocol analysis will not be our primary analysis, and we will report in detail the criteria for exclusion of individuals.

If we encounter missing data due to drop out or assay issues, we will apply mixed model regression using the available data in the analysis. In general, our analysis based on available data will be similar to the analysis using the individuals who do not have missing data (complete-case analysis) if the missing data mechanism is completely at random (108). When the

Protocol 10045

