13.3 Sample Size and Power

98 individuals will be randomized. Accounting for up to 20% drop-out, power calculations are based on 78 participants.

Table 1. Minimum detectable absolute difference in mean change from baseline to 24 weeks between two groups (n=39 for Control group and n=39 for Exercise group) for the study endpoints, given an intra-individual correlation (ρ) of 0.5, 0.65 or 0.8, at 80% power, and adjusting for the number of hypotheses tests with 7 primary endpoints (type I error of 0.05/7).

Endpoint	Mean	SD	Minimum detectable absolute difference (% change)		
			$\rho = 0.5$	$\rho = 0.65$	$\rho = 0.8$
Distress (Perceived Stress Scale) ^a	19.23	6.77	5.41 (28.16%)	4.53 (23.56%)	3.42 (17.81%)
Distress (Hospital Anxiety and Depression Scale-anxiety subscale) ^b	7.4	3.9	3.12 (42.15%)	2.61 (35.27%)	1.97 (26.66%)
Distress (Hospital Anxiety and Depression Scale-depression subscale) ^b	5.8	3.5	2.87 (48.26%)	2.346 (40.4%)	1.77 (30.52%)
Quality of Life (36-item Short Form Survey- Physical Component Score) ^c	45.6	9.2	7.36 (16.14%)	6.16 (13.5%)	4.65 (10.21%)
IL-6 (pg/mL) ^d	2	0.7	0.56 (27.99%)	0.47(23.42%)	0.35 (17.70%)
VEGF (pg/mL) ^e	192	158.2	126.5 (65.88%)	105.8 (55.12%)	80(41.67%)
Salivary cortisol (nmol/L) ^d	4	0.6	0.48 (12.0%)	0.4 (10.04%)	0.3 (7.59%)

Mean and SD obtained from: ^a Perceived Stress Scale score in ovarian cancer survivors at the end of primary chemotherapy (111), ^b Hospital Anxiety and Depression Scale anxiety and depression subscale scores in ovarian cancer survivors towards end of primary chemotherapy (112), ^c 36-item Short Form Survey- Physical Component Score in our randomized controlled trial of exercise in ovarian cancer survivors (17), ^d biomarker levels in ovarian cancer survivors 6 months after primary treatment(113), and ^e VEGF levels in ovarian cancer survivors after completion of primary chemotherapy (114).

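### The maintenance-therapy subgroup analysis in 13.7 has no interaction term and no status fixed at randomisation, so it cannot say whether the exercise effect differs between groups

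*Combined protocol and SAP*

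**What the plan says.** Section 13.7 extends the primary-analysis GEE models to "additional exploratory subgroup analyses to assess the intervention effects on the primary outcomes by chemotherapy maintenance group", with the condition "if the sample size is sufficient". The companion analysis in the same section looks at the intervention effect "among participants who developed (versus those who did not develop) recurrence over the course of the study".

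The model is set out in 13.2. It has terms for time, arm, arm by time, and covariates. The effect parameter β₁ is the arm-by-time coefficient, which "represents the mean difference in the outcome change from baseline to follow-up between participants in the exercise group and participants in the control group". The covariate term Z is introduced to "represent a vector of other potential adjusting variables (such as age, BMI") and enters as main effects only. Inference is by "two-sided Z-test and Z-confidence intervals based on the limiting Gaussian distribution".

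The only significance level stated is the one behind Table 1 in 13.3, "adjusting for the number of hypotheses tests with 7 primary endpoints (type I error of 0.05/7"). Section 5.1.3 says "Maintenance therapy will be allowed as long as the participant is in clinical remission", and names hormonal agents, anti-angiogenesis agents, PARP inhibitors and immunotherapy.

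The plan nowhere gives an arm-by-time-by-maintenance term, an interaction test, a significance level for subgroups, an expected share on maintenance, or a rule for interpreting the subgroup results.

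**The concern.** Asking whether exercise works differently in women on maintenance treatment is a question about a difference between two effects. The 13.2 model has no parameter for that difference. Applied by group, it gives a β₁ and a p-value for each group. If maintenance were only added to Z, it would give no group-specific effect at all. Neither use estimates how far the effects differ.

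The output then invites a comparison of p-values: significant in one group, not in the other. Subgroups of this size have moderate power, so that pattern can arise often when the true effects are equal.

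Group membership is also open. The label in 13.7 refers to chemotherapy maintenance, while 5.1.3 lists several kinds of agent, and nothing says which count. Nor does 13.7 say when status is taken. Section 7.3 permits any care during the study and section 9.0 lets women with recurrence continue, so status can change after randomisation. Groups formed on later status would not be baseline groups, and the arm comparison within them would lose the protection of randomisation. Maintenance is not a randomisation factor either: 13.4 uses stage and BMI.

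**Working it through.** **Inputs from the documents.** 39 analysed per arm, 80% power, two-sided 0.05/7, and ρ of 0.5, 0.65 or 0.8 (13.3). SDs of 6.77 for the Perceived Stress Scale and 9.2 for the SF-36 physical component score (Table 1). Earlier randomised exercise trial: mean changes of 1.8 and −2.0 on the physical component score (2.3), a difference of 3.8 points.

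**Assumptions, not in the documents.** The maintenance split; the same true effect in both groups; 0.05 as an alternative subgroup level; and an apparent difference meaning that exactly one group is significant.

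**Step 1: reproduce Table 1.** SD of change = SD × √(2(1−ρ)), which equals SD at ρ = 0.5. Detectable difference = (2.690 + 0.842) × SD of change × √(2/39) = 3.532 × 0.2265 × SD of change = 0.80 SD of change.

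- Perceived Stress Scale: 0.80 × 6.77 = 5.415 with unrounded factors (stated 5.41).
- Physical component score: 0.80 × 9.2 = 7.358 with unrounded factors (stated 7.36).

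The stated differences give power within 2 points of 80% in 20 of the 21 cells. The exception is HADS-depression at ρ = 0.5: 2.87 is stated, but its own 48.26% of 5.8 is 2.80. This does not affect the check.

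**Step 2: power within a subgroup.** If the full-sample standardised effect is θ, a subgroup holding share f has mean Z of θ√f. With θ = 3.532 and f = 0.5, mean Z = 2.497.

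- At 0.05: power = Φ(2.497 − 1.960) = 70.4%.
- At 0.05/7: power = Φ(2.497 − 2.690) = 42.4%.

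**Step 3: chance that exactly one subgroup is significant**, p₁(1−p₂) + p₂(1−p₁). At 50:50 and 0.05 this is 2 × 0.704 × 0.296 = 41.6% (41.7% in a 200,000-replicate simulation). At 0.05/7 it is 2 × 0.424 × 0.576 = 48.8%.

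For the earlier trial's effect, θ = 3.8 / (9.2 × √(2(1−ρ)) × 0.2265), which is 1.82, 2.18 and 2.88 at ρ = 0.5, 0.65 and 0.8.

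| True effect, equal in both groups | Split | At 0.05 | At 0.05/7 |
|---|---|---|---|
| Table 1 difference | 50:50 | 41.6% | 48.8% |
| Table 1 difference | 70:30 | 50.7% | 55.7% |
| Table 1 difference | 90:10 | 75.0% | 71.7% |
| Half the Table 1 difference | 50:50 | 36.4% | 13.8% |
| 3.8 points, ρ = 0.5 | 50:50 | 37.7% | 14.8% |
| 3.8 points, ρ = 0.65 | 50:50 | 44.8% | 21.9% |
| 3.8 points, ρ = 0.8 | 50:50 | 49.8% | 38.2% |
| None | any | 9.5% | 1.4% |

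With no dropout (98 analysed), the Table 1 difference at 50:50 gives 32.1% at 0.05.

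**Step 4: the interaction test.** With equal effects it errs at its nominal rate: 5%, or 5.4% in simulation with estimated variances and Z critical values at 19–20 per arm per subgroup. Its standard error is √(2/n₁ + 2/n₂) SD of change, where n₁ and n₂ are the per-arm subgroup sizes. The difference detectable with 80% power at 0.05 is 2.80 times that:

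- 50:50: 2.80 × √(2/19.5 + 2/19.5) = 1.27 SD.
- 30:70: 2.80 × √(2/11.7 + 2/27.3) = 1.38 SD.

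For a between-group difference as large as the whole Table 1 difference at 50:50, mean Z = 3.532/2 = 1.766. Power is 42% at 0.05 and 18% at 0.05/7.

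**The case against.** The strongest reply is that the plan underspecifies this analysis rather than stating a wrong one. It is labelled exploratory, is neither an objective nor a listed endpoint, and depends on adequate numbers. Much of this stands, and it limits four stronger readings.

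- A reader might infer that the plan prescribes separate refits. It does not say so. Separate fitting is the natural reading, supported by the wording of the recurrence analysis beside it, but a single model with a maintenance term is not excluded.
- A reader might infer that equal effects will look different about 40% of the time. That needs an even split, a real effect of Table 1 size in both groups, a 0.05 level and a reading by significance. The plan fixes none of these for this analysis, and the cases above run from about 1% to 75%.
- A reader might compound the per-endpoint figure over seven endpoints and call a false contrast nearly certain. That assumes independent endpoints that all carry a sizeable effect. Three of the seven are distress scales in the same women, and the 3.8-point effect concerns the physical component score alone.
- A reader might infer that this subgroup result will drive the larger trial. Section 2.1 says the study's data will justify such a trial and does not mention maintenance treatment.

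The sample-size condition could rule out the most uneven splits: at 30:70 the smaller group has about 12 women per arm. But it sets no threshold and does not say how a difference would be judged. The low power of the interaction test is also true. It calls for reporting an interval, not for leaving the comparison to two p-values.

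**Conclusion.** The point holds as a gap in an exploratory analysis that should be closed. As written, 13.7 produces no estimate of whether the exercise effect differs by maintenance group, and it leaves membership and its timing undefined. This follows from the text and needs no assumption about numbers.

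The consequence is conditional. If readers compare significance across groups and the split is even, equal effects appear different 42% of the time per endpoint at 0.05 for the Table 1 effect (49% at 0.05/7). For the earlier trial's physical component effect, over ρ = 0.5 to 0.8, the figure is 38–50% (15–38% at 0.05/7). With no effect it is 9.5% (1.4%). Because the documents give no maintenance share, these figures illustrate the risk and do not predict it. The primary analysis is not affected.

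**What to change.** In 13.7, for each primary endpoint, specify one GEE model with maintenance status at randomisation (M), arm (X), time (j) and all their interactions:

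E[Y] = α₀ + α₁j + β₀X + β₁Xj + γ₀M + γ₁Mj + δ₀MX + δ₁MXj, plus Z in the adjusted version.

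- Report δ₁ with its confidence interval as the subgroup result.
- Show the within-group effects, β₁ and β₁ + δ₁, with intervals as description only and without within-group p-values. With complete data and no covariates they match the separate-fit estimates, so nothing is lost.
- Define which of the agents in 5.1.3 count as maintenance.
- Take status from the baseline medical record review (15.3) together with the baseline medication assessment (8.1). The latter rests on participants' lists and labelled containers and could miss agents given in clinic.
- State that the interaction is imprecise: 80% power at 0.05 only for a difference of about 1.3–1.4 SD of change. A wide interval is then not read as evidence of equal effects.

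The cost is a few sentences in 13.7. Both data sources are already in the plan, and no extra visits or participants are needed.
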